10.6 Statistical analysis

10.7 Summary of baseline data and flow of participants

Baseline variables: Room used (categorical), clinician in the room (categorical), mean number of patients seen in time period and standard deviation, mean age and proportion of patients of each sex, mean number of accompanying persons per time period. A consort flow diagram will be generated for each trial stage.

10.8 Primary outcome analysis

Data analysis will be linear mixed modelling of the paired data (3 conditions for each clinician) controlling for confounding factors which may include: number of people in the room, baseline ventilation, room size, room shape, temperature, humidity and various other factors (see full list of suggested confounding factors in study design section). The power of the trial based on the UK sites alone is 90%.

Data analysis relies on properly functioning aerosol generators and particle counters. In stages 1 and 2, we will check each piece of machinery is working properly before the beginning of the clinical session. Where we do not manage to collect data for at least 2 hours in a clinical session, that session will be withdrawn from the study and repeated in its entirety. We expect this to happen in less than 5% of clinic sessions. For stage 3, a minimum of 6 hours data per day is required otherwise that day's randomisation will need to be rerun.

There are no plans for predefined subgroup analyses in stages 1 and 2. For stage 3, subgroup analyses will include daytime (8 am to 8pm) versus nighttime (8 pm to 8 am).

We will employ the intention-to-treat (ITT) analysis method to ensure the integrity and validity of our RCTs.

Whereas a standard cost-effectiveness ratio reports the mean incremental cost per change in outcome, averaging across units, we have chosen DEA analysis to better reflect the heterogeneity in efficiency across rooms and hospitals. Similar to cost-effectiveness analysis it is used in situations where the unit of output, in this case reduction in droplets, has no natural market value³¹. DEA is particularly useful in ranking and hence will help us identify the maximum efficiency of the AISaT in hospital consultation rooms and wards; information that could then potentially be contrasted with the efficiency of full installations of air filters.

The decision making units (DMU) will be defined as the room or ward where AISaT mitigations are being put in place. The definition of a DMU is important in DEA as it determines the units to be compared to each other and ranked. As different rooms/wards may have different efficiency based on a wide range of factors, from the room itself to clinician and patient behaviour, it makes sense to make them the DMU. Given that consultation rooms and wards will have very different input costs and potentially output the two will be analysed separately. They will also have different units of

analysis for costs, with the unit of analysis for wards being bed days and the unit of analysis for consultations number of patients seen. The output will be the ratio of droplets removed with and without AISaT mitigations. This is likely to result in data points across multiple 60 minute time windows for the different units with and without AISaT, which is likely to be a sufficient sample size to conduct the analysis, although consideration will be made as to the impact of sample size changes by partitioning the data on the results³³. Inputs will include the number of HEPA filters, screens and fans in the room and the cost per hour to run the system based on the cost of electricity to run the HEPA filters. Costs for clinical or engineering staff time in training and installation and any fixed costs for the AISaT system will also be included in the inputs. DEA then is concerned with identifying the maximum output (ratio of droplets removed) for minimal cost. In this case we will look at cost per consultation and cost per bed day.

We will also consider allocative efficiency, in regards to cost-effectiveness. Using similar input and outputs as in the technical efficiency analysis, we will calculate marginal costs per patient seen, per session or per bed day as appropriate when AISaT is used compared to current practice. We will look at the literature to determine the evidence for the relationship between droplet reduction and the reduction in infections for both ward bed days and consultations. This is likely to be based on the D50, or the mean dose of an infective agent required to cause an infection in 50% of susceptible individuals, with the D50 of Influenza-A for example estimated at 790 viral copies³⁴. The relative reduction of air droplets is then used to estimate the reduction in viral copies in the air and hence the reduced risk of infection³⁵. There is ongoing evidence generation occurring in this field, so we will revisit the literature at the point of analysis to determine the best evidence base for the relationship between droplet removal and reduced risk of infection. The predominant infectious diseases and their incidence also change over time, and hence the values modelled will need to reflect the state of play at the time of analysis. The marginal cost of AISaT will then be contrasted with the cost of reduced infections, calculated based on the average cost per infection treated as obtained from the literature. We will also search the literature for any evidence of impact on quality adjusted life years (QALYs) as a result of reduced infections.

10.10 Sensitivity and other planned analyses

At the end of the clinic, a member of the research staff will ensure that there was compliance to the randomised setting and a log will be kept in order to track this data. The measurements will be reviewed for reliability.

At the end of each pilot phase, an interim statistical analysis will be performed to assess whether the main study is likely to meet the study goals.

Data analysis will be linear mixed modelling of the data controlling for confounding factors. Sensitivity analyses will remove measurements that are considered potentially, or definitely, unreliable. These analyses will be compared to the analyses that keep all collected data points. Interpretation of the main findings

Full data analysis will be undertaken by our co-I at CCTU and his team at the end of each stage of the clinical trials and will again perform data analysis using linear mixed modelling of the data (3 conditions for each clinician) controlling for confounding factors.

Decision criteria used to judge the interim results as part of a guideline for early stopping

Each trial is due to complete within 6 months, with a 3 month buffer to deal with unforeseen problems. The pilot phase for the first trial in consulting rooms will recruit 20% of the patients in 5 weeks. The trial will STOP if we don't recruit 60% of expected number (i.e. 12% of the total recruitment).

The AlSaT tool may not be able to compute a solution to reduce aerosol transmission in the rooms we wish to use for trial. If this occurs, the TMG will allow an extra 3 months to find rooms that the tool can be used in. If we cannot find suitable clinic rooms, TMG will stop the trial.

A report will be produced by engineering team at end of each pilot on numbers of aerosol droplets measured. Trial statisticians will ensure it will be possible to determine statistically whether the trial could reach predefined end points. If not, TMG will discuss with engineering team how to seed the room with more droplets and then implement. Although unlikely that doctors or patients will notice changes, we will perform a further pilot. TMG will stop second trial if we cannot recruit adequately during pilot as above. The statistical report at the end of each pilot will identify variance in aerosol droplet concentrations between the clinical areas. Even apparently identical rooms may have different airflows. If current sample size inadequate to achieve statistical power needed, statisticians will advise the TMG of a new sample size. TMG to discuss with trial team extra patient recruitment. If unachievable within 9 months, TMG will stop trial. At the end of each pilot, trial team will also ask hospital staff whether AI generated mitigations interfere with clinic, procedure room or ward e.g. due to noise or trip hazards. TMG will discuss with engineering team adjusting AlSaT system. If not achievable, trial will be stopped. Ensuring adequate research support staff to run trials. This is costed in SoeCAT. We know that NHS Trusts are under pressures and may not have research staff available to enable recruitment. If recruitment in pilot phase is too low, TMG will decide whether to stop the trial at that point. For trial stage 2, based in procedure rooms, the issues above remain relevant. Ventilation rates are higher than in standard consulting rooms, and there is more movement of people as well as intermittent aerosolising equipment use and use of personal protective equipment (PPE) by staff. All these factors may increase standard deviation in aerosol droplet levels. Study sample size may therefore need to be larger, but we will apply the same stop/go criteria as for trial stage 1. All issues above remain relevant in the ward bay trial stage 3. Here operational risks are key. Ward changes happen for many reasons and are impossible to predict. If a change to wards is needed, the statisticians will advise whether this will impact on trial delivery. If not possible to complete within the time frame, TMG will decide whether to stop the trial.

Management

The trial team will report to the trial management group (TMG) at the end of week 5. If recruitment is inadequate, TMG will discuss with the trial team why recruitment failed and explore ideas to improve recruitment before deciding on whether to restart. Discussions may also be had with our programme PPIE panel. The trial will restart if TMG confident it can complete recruitment within 9 months.

Who will see the outcome data while the study is ongoing?

The operational trial staff will collect and collate the data while the study is ongoing. The trial statisticians will also see the data and will share it with the TMG if necessary, according to the stop criteria listed above.

Whether these individuals will remain blinded to the trial groups

This is an unblinded trial. The statistician will be responsible for producing the randomisation lists, and so will not be blinded.

How the integrity of the trial implementation will be protected (e.g. maintaining blinding) when any adaptions to the trial are made

We will involve key stakeholders, including the trial statisticians, early in the design planning process for any trial adaptations. This will help us anticipate potential challenges and develop robust blinding procedures. We have pre-specified in the protocol pilot phases for each trial stage. These allow for interim analyses and implementation of decision rules for adaptations such as stopping the trial early for efficacy or futility, adjusting sample sizes, or modifying treatment arms. By pre-specifying these adaptations, we will ensure that changes are made systematically and transparently, whilst maintaining the integrity of trial implementation.

Who has the ultimate authority to stop or modify the study e.g. the CI, Trial Steering Committee, or the Sponsor?

The ultimate authority to stop or modify the trials lies with the trial steering committee, to whom the CI is answerable.

Stopping criteria for futility are described earlier in this section.

Stopping criteria for harm include if participants experience significant adverse health effects that are directly attributable to the study. These might be due to unexpected problems such as trip hazards, patients throwing filters etc (particularly in the stage 3 study) or if device malfunctions cause risks to participants. In all of these cases, an adverse event report will be completed and the CI, in consultation with the TMG and/or the TSC will decide whether to terminate the study early.

The strategies to maximise follow-up and prevent missing data

No follow-up is required. We will collect only essential information to reduce participant burden. Strategies to minimise the risk of missing data include ensuring that CRFs are user-friendly, and electronic CRFs will have mandatory data fields and data validation checks. We will also provide

thorough training to the clinical trials staff to ensure that they check CRF data at the time they are completed. The pilot study phases will also identify potential issues before the main studies begin.

How recording of reasons for missing data will be undertaken

Recording reasons for missing data will be undertaken using standardised forms to capture these reasons. The forms will be developed and iterated throughout the pilot phases and as the trials progress. Study personnel will also be trained regularly and encouraged throughout the trials to document reasons for missing data in a detailed way. This includes noting the specific circumstances and any relevant participant feedback when data is missed.

Where participant interviews are undertaken, follow-up interviews will be offered to those who miss appointments or data collection points. This will help the study team gather insights into the reasons for missing data and address any issues that may prevent future participation.

Finally, regular monitoring and audits will be undertaken to review the completeness and accuracy of the recorded reasons for missing data.

How missing data will be handled in the analysis and whether there are any planned methods to impute missing outcome data, including which variables will be used in the imputation process

Initially, we will perform a complete-case analysis, where only participants (clinicians or ward bays) with complete data from all entire study periods are included. This approach helps to understand the extent and pattern of missing data. We will then conduct sensitivity analyses to assess the impact of missing data on our results. This includes comparing the results of complete-case analysis with those obtained using imputation methods.

We will use multiple imputation (MI) to handle missing data. MI involves creating multiple datasets by imputing missing values based on observed data, analysing each dataset separately, and then combining the results to produce final estimate. Full information maximum likelihood (FIML) will be used as an alternative method, which estimates model parameters directly using all available data without imputing missing values.

The imputation process will include the following variables to ensure accurate and unbiased estimates: **Baseline Characteristics:** Age range, sex, body size, **Outcome Measures:** Primary outcome measure of respiratory particle counts. **Auxiliary Variables:** Additional variables that are correlated with the missing data and the outcomes, such as environmental factors and room conditions will be analysed.

The procedure for reporting any deviation(s) from the original statistical plan

We will document deviations, including details of the nature, reason and potential impact of the deviation on the study outcomes.

Significant deviations that may affect the study validity, reliability, or participant safety will be reported immediately to the TMG and the study sponsor and will also be reported to the TSC. The PI and local study team will conduct an assessment and root cause analysis of the deviation. This involves identifying who deviated from the protocol, what the deviation was, when and how it occurred, and its impact on the study. Based on the assessment, an action plan will be developed to address the deviation. This plan will include steps to mitigate any negative impact and prevent similar deviations in the future.

Minor deviations (which are not considered to be adverse events for participants) will be documented and reported to the TMG during regular progress reports. All deviations and the corresponding action plans will be transparently reported in the final study report and any publications resulting from the study to make the scientific community aware of changes to the original statistical plan.

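### Readings judged definitely unreliable are removed only in sensitivity analyses, so the main analysis, read from sections 10.8 and 10.10 together, keeps known instrument failures

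*Protocol*

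**What the plan says.** All references are to the protocol.

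- **Section 10.10, review of readings.** "The measurements will be reviewed for reliability". The reviewer is not named, and the review is not linked to any exclusion from the main analysis.
- **Section 10.10, what is removed, and where.** "Sensitivity analyses will remove measurements that are considered potentially, or definitely, unreliable". The next sentence gives the comparator: "These analyses will be compared to the analyses that keep all collected data points".
- **Section 10.8, premise.** "Data analysis relies on properly functioning aerosol generators and particle counters".
- **Section 10.8, equipment check.** "In stages 1 and 2, we will check each piece of machinery is working properly before the beginning of the clinical session". No such check is stated for stage 3.
- **Section 10.8, minimum data, stages 1 and 2.** "Where we do not manage to collect data for at least 2 hours in a clinical session, that session will be withdrawn from the study"; it is then repeated. On how often: "We expect this to happen in less than 5% of clinic sessions".
- **Section 10.8, minimum data, stage 3.** "For stage 3, a minimum of 6 hours data per day is required otherwise that day's randomisation will need to be rerun".

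The primary outcome (sections 3.3 and 10.1) is the average droplet count per minute per clinical encounter, from a counter beside the clinician and up to four others. Section 10.8 also commits to intention-to-treat.

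**The concern.** Section 10.8 makes valid measurement a condition of the analysis, but the rules that follow test only whether the equipment works at the start and whether enough data were collected. Neither detects a generator that stops, or a counter that drifts or saturates, partway through a session while readings continue. The reliability review in section 10.10 could detect this, but its result is used only in sensitivity analyses.

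Each clinician gives one session per configuration, so one corrupted session distorts two of that clinician's three pairwise contrasts. These within-clinician contrasts are what the crossover relies on. At stake are the precision of the primary result and, if faults are more frequent or larger under one configuration, its direction.

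Intention-to-treat does not require the present rule. It keeps randomised units in their allocated sequence; it does not require a known instrument failure to be analysed as a droplet count.

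**Working it through.** **1. Which analysis keeps the faulty readings?** A sensitivity analysis is compared with the main one. Section 10.10 compares its sensitivity analyses with analyses that retain everything collected, and section 10.8 has no validity exclusion. Two rules elsewhere do remove data: sessions under 2 hours are withdrawn (section 10.8), and time with a non-consenting patient is not used (section 5.3). These concern quantity and consent, not validity. So the main analysis keeps definitely unreliable readings.

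**2. The plan's own figure.** Inputs from section 10.3: means 0, 0.25, 0.5; SD 1; correlation 0.5 (compound symmetry); alpha 0.05.
- Sum of squared deviations of the means: 0.25² + 0 + 0.25² = 0.125.
- Within-clinician variance: 1 × (1 − 0.5) = 0.5.
- Noncentrality λ = n × 0.125 / 0.5 = 0.25n; F-test on 2 and 2(n − 1) degrees of freedom.
- n = 52 gives power 89.9%, n = 53 gives 90.5%, n = 54 gives 91.1%. The stated 53 reproduces.

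**3. Effect of a fault on one session.** Section 10.4 expects about 3 analysable hours per 4-hour session. If 1 of the 3 hours reads k times the true level, the session mean is multiplied by (2 + k)/3.
- Generator off, no background (k = 0): 0.67, a fall of 33%.
- Threefold readings (k = 3): 1.67, a rise of 67%.
- Tenfold readings (k = 10): 4.00, a rise of 300%.

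In each case 2 good hours remain, so the session meets the minimum.

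**4. Illustrative effect on power, stages 1 and 2.** These inputs are assumptions, not protocol figures: a fraction f = 5% of sessions is affected, at random and equally in all configurations; session SD is 50% of the mean (so the mean is 2 SD); one counter determines the session value. The shift in SD units is S = proportional change / 0.5. Within-clinician variance becomes 0.5 + f(1 − f)S², and λ = 54 × 0.125 / that variance = 6.75 / variance.

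| Fault | S | Variance | λ | Power |
|---|---|---|---|---|
| None | 0 | 0.500 | 13.50 | 91% |
| Generator off | −0.67 | 0.521 | 12.95 | 90% |
| Threefold | 1.33 | 0.584 | 11.55 | 86% |
| Tenfold | 6.00 | 2.210 | 3.05 | 32% |

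Simulating the same F-test with randomly shifted sessions gives 90%, 86% and 33–35%.

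**5. How far the assumptions matter.**
- SD 25% or 100% of the mean: generator off about 86% or 91%; threefold about 71% or 90%; tenfold about 13% or 66%.
- Fault rate 1% (SD 50%): threefold 90%, tenfold about 70%.
- Five counters averaged, one faulty (5%, SD 50%): S falls to 0.27 or 1.20, giving 91% for threefold and 87% for tenfold.

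**6. Bias.** With equal fault rates the shift cancels between configurations. If rates differ, the bias is the difference in rates times S. For example, 5% against 0% with threefold readings gives 0.05 × 1.33 = 0.07 SD, compared with the planned step of 0.25 SD. Its sign depends on which configuration is affected and whether the instrument reads high or low.

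Stage 3 has no formal sample size (section 10.4), so no power figure is offered for it.

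**The case against.** The strongest defence is that the protocol already plans a reliability review, both analyses and their comparison, and that keeping all data in the lead analysis guards against selective deletion in a trial whose participants are not blinded. That stands for doubtful readings, which can properly stay in the primary analysis. It does not stand for readings established as instrument failures: criteria fixed in advance and applied without knowledge of configuration give the same protection.

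It can also be said that the 2-hour rule, coming straight after the sentence on working equipment, means 2 hours of valid data, and that section 10.4 speaks of analysable data. The reading is possible, but section 10.8 does not say so, and even then it would not remove the invalid minutes of a session that qualifies.

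A reader might infer more than the documents support:
- **That the keep-all analysis is labelled primary.** It is not. This is an inference from the contrast in section 10.10 and the absence of an exclusion in section 10.8.
- **That the two grades must be dropped together.** Section 10.10 refers to analyses in the plural, so one analysis per grade is equally possible.
- **That reliability is graded by staff who know the configuration.** Staff check compliance with the setting, but no reliability reviewer is named.
- **That absent fault definitions are an error.** Such detail commonly sits in a statistical analysis plan, which is not at hand.
- **That faults would favour AISaT.** No reason is given for faults to differ by configuration, and an under-reading counter in a no-mitigation session would work against AISaT.

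**Conclusion.** The point holds as a rule the protocol states, not as a silence: definitely unreliable readings leave the data only in sensitivity analyses, against the premise of section 10.8. It should be changed, but it is moderate in weight because an analysis without these readings is already planned.

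On the assumptions shown, the cost ranges from about 1 point of power (generator off) to about 5 points (threefold readings from a single counter). It is more for extreme faults and less if several counters are averaged or faults are rarer. The tenfold results should not be taken as a forecast: they need an hour of gross error in 5% of sessions, with one counter driving the session value. The below-5% figure in section 10.8 concerns sessions withdrawn and repeated, so it does not support a 5% rate of faulty sessions that are kept. The generator case applies only where one is used; section 4 makes this depend on the pilot, although the study summary says one will be installed. Counter faults apply either way.

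Nor is the planned sensitivity analysis necessarily the correct estimate, since it may also drop doubtful but valid readings.

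**What to change.** In sections 10.8 and 10.10:

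1. Treat definitely unreliable minutes as missing in the primary analysis. Identify them by objective instrument criteria fixed in advance and applied without knowledge of configuration. The criteria themselves can sit in the statistical analysis plan.
2. Keep potentially unreliable minutes in the primary analysis and remove them in a separate sensitivity analysis.
3. Report the all-readings analysis as a further sensitivity analysis.
4. State that the 2-hour and 6-hour minima count valid minutes.
5. Name the role that grades reliability. Sections 7.2 and 12.10 describe the statistician as blinded and section 10.10 says the opposite, so it is not clear at present who could grade blind.

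The cost is mostly wording. Some session means will rest on fewer minutes, a few more sessions may need repeating, and instrument status must be recorded over time if it is not already; the protocol mentions a compliance log but no instrument log. The methods for missing data in section 10.10 can take the removed minutes.
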